Pharmacokinetic Studies (required) May be collected through the line used for Marqibo® infusion.			Immediately prior to Marqibo administration for Marqibo doses #1, 2, and 3 for arm A and B.	Arm C will be obtained prior to Dose 1 and a trough level on day 8, during each cycle.	

STUDIES TO BE OBTAINED	Pre-Enrollment*	Pre-Treatment (within 3 days prior to starting protocol therapy)	During Course 1 (Cohort A and B)	During Course 1 (Cohort C)	Final Visit/ Follow-up
Peripheral Blood for Pharmacokinetic Studies (optional)			Day 1 (3 blood samples)	Day 1 (3 blood samples)	
Follow-up visit					Q 6months

*Required for verification of eligibility. FAX or email all results to the TACL Operations Center with study registration eligibility. If a patient has labs done prior to study entry that establish eligibility, then abnormal Day 1 labs do not deem them ineligible.

#Optional

^Within 2 weeks prior to enrollment is acceptable

†IT chemotherapy is not required at the time of day 29 LP, but can be given per investigator discretion.

§Cohort C disease restaging will be done after cycle 1, if only one cycle is administered. If a second cycle is planned, restaging may be done after cycle 2. Please see section 7.3 for additional guidance. A lumbar puncture will only be required after 2 cycles; and is optional after cycle 1.

1: BUN, creatinine, ALT, AST, LDH, alkaline phosphatase, glucose, total and direct bilirubin, albumin, total protein, uric acid

2: Sodium, potassium, chloride, bicarbonate, calcium, magnesium, phosphorus

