7.4.2 Marqibo® Pharmacokinetic Studies (Mandatory and Optional Studies)

Participation in PK studies is mandatory for a limited set, for which samples can be drawn from the same line used to administer Marqibo®. These studies include a baseline level drawn prior to the first dose and trough levels prior to the second and third dose of

Marqibo®. Participation in more detailed PK studies, which require samples to be drawn from a separate line than the one used to administer Marqibo® are voluntary. (Appendix 7).

The mandatory PK samples will be collected at the following time points for arm A and B.

- Generally performed 30-60 minutes before start of dose 1 infusion (SOI) ±10 minutes, but may be performed with routine morning labs as long as it is before start of infusion.
- Pre-dose #2 (trough level), up to 1 hour pre-dose is acceptable
- Pre-dose #3 (trough level), up to 1 hour pre-dose is acceptable

For cohort C, the mandatory PK samples will be drawn 30-60 minutes before start of dose 1 infusion (SOI) ±10 minutes, but may be performed with routine morning labs as long as it is before start of infusion; and a trough level will be drawn anytime on day 8.

The voluntary PK samples will be collected at the following time points (all cohorts):

- End of Infusion (EOI) of dose 1 ±5 minutes
- 3 hours (EOI + 2 hours) ±15 minutes
- 25 hours (EOI + 24 hours) ±30 minutes

Analysis will be conducted in the laboratory of the NCI POB Pharmacology and Experimental Therapeutics program. Quantification of total plasma vincristine will be performed by a qualified LC/MS/MS.

Samples requested:
	
Mandatory (Arm A & B)
 
 • Pre-dose 1 • Pre-dose #2 (trough level) • Pre-dose #3 (trough level) 
May be collected through the line used for Marqibo® infusion
 
Mandatory (Arm C)
 
 • Pre-dose 1 • Day 8 will have a trough level 	
Voluntary (all cohorts)
 
 • End of infusion (EOI) of dose 1 • 3 hours (EOI + 2 hours) • 25 hours (EOI + 24 hours) 
Must be collected from a separate line from that used for Marqibo® infusion.

----------------------------------	--	---

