9.0 STATISTICAL CONSIDERATIONS

The Phase I sample size for each dose level and each of the three cohorts is 6 evaluable patients for the primary endpoint, consistent with the sample size typically sufficient to demonstrate regimen tolerability in Phase I trials. The maximum sample size in any cohort at a particular dose level is 12 evaluable patients, including 6 evaluable patients for expansion.

As of Protocol Amendment #3, Cohort A will enroll at DL1 only. Cohort B will utilize DL1 and Cohort C will continue treatment at DL2. Dose escalation for Cohort B and de-escalation for Cohort C may still occur per study design.

The focus of the study design and statistical analysis is to determine whether Marqibo® can be substituted for standard vincristine and successfully administered to patients with relapsed ALL in three different treatment cohorts: (A) treatment with the UK ALL R3 regimen; (B) treatment with UK ALL R3 regimen without mitoxantrone, and (C) treatment with ALL maintenance therapy. Secondary objectives include estimating rates of serious toxicities and therapy delays in each of these cohorts. Achievement of response and achievement of an MRD undetectable status will only be evaluated in Cohorts A and B, as Cohort C is not being used to eradicate disease, rather is only intended for the purposes of disease stabilization.

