9.4.4 Pharmacokinetics analysis: The precision with which a detailed pharmacokinetic analysis of vincristine levels after exposure to Marqibo® in the context of UK ALL R3 treatment or maintenance therapy in this population of patients can be performed will depend on the number of patients who participate in the optional Day 1 PK component of this study, which includes sampling at end of infusion, 3 hours and 24 hours in addition to the mandatory day 8 and day 15 samples (applicable to only the UK ALL R3 with or without mitoxantrone arms A & B). Patients enrolled to arm C will only have pre-dose #1 (30 minutes before start of infusion (SOI) and a trough level at day 8 during the first cycle. Assuming first order elimination, these pharmacokinetic analyses will include estimation of total vincristine concentration, area under the curve through 168 hours, and, the half-life of vincristine when Marqibo® is given with combination therapy. However, the two mandatory samples at day 8 and 15 taken prior to the second and third dose of Marqibo®, representing vincristine trough levels, will be obtained on all patients. There are no data currently available to estimate interpatient variability of vincristine levels from Marqibo® in children, but data from²³ in adults indicate that the coefficient of variation (CV) of vincristine at trough levels will be approximately 100%. Hence, assuming that the study proceeds to the second stage, and that 25/30 patients are evaluable for PK assessment, the precision of the estimate of mean trough levels of vincristine at each of these times point will be CV=17%, resulting in a 95% confidence interval with bounds within 40% of the population value. This provides sufficient precision for meaningful comparison of vincristine concentration in this study to published adult study as well as the ongoing Marqibo® Phase I study in children. These analyses will be based on the total vincristine exposure and will not include distinguishing between the free and liposomal bound components.

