APPENDIX 7: PHARMACOKINETIC WORKSHEET – T2012-002 MARQIBO® Study

TACL Registration #: _____ BSA (m2): _____
Height (cm): _____ Assigned Dose (mg/m²): _____
Weight (kg): _____ Actual dose (mg): _____

Dose 1:

Date of Administration	Infusion Start Time	Infusion End Time
_____	_____	_____

Dose 2 (arm C will have a trough level but no dose administered¹):

Date of Administration	Infusion Start Time	Infusion End Time
_____	_____	_____

Dose 3 (Not required for Arm C)

Date of Administration	Infusion Start Time	Infusion End Time
_____	_____	_____

1. Complete a second form if there is a second cycle of Arm C

Sample #	Day	Date	Hour	Target Time	Time obtained	Comments
----------	-----	------	------	-------------	---------------	----------

1	1		All: Pre-Dose			
2*	1		Arm A/B: End of Infusion (EOI)			
3*	1		Arm A/B: EOI + 2 hours			
4*	1		Arm A/B:EOI + 24 hours			
5	8		All: Pre dose #2 (trough level for Arm C)			
6	15		Arm A/B: Pre dose #3			

EOI = End of infusion. * Obtain sample, if feasible, in consenting patients from a line separate than the one used to infuse Marqibo®

Blood Sample Collection and Processing

- For non-mandatory samples, a peripheral or central access device may be used for collection of the PK samples. This must be a separate line from that used for Marqibo® infusion.
- Mandatory PK samples may be collected through the line used for Marqibo® infusion.
- If blood samples are taken via an indwelling central venous cannula, an appropriate amount of fluid should be removed from the cannula to clear the line before each blood sample is taken.
- Blood samples of 3 mL will be collected in lavender-top (EDTA) vacutainers at each of the time points indicated above. Invert the lavender-top vacutainer 10 times to mix completely.
- Complete the labels using a waterproof pen and apply to the Vacutainer tubes. Complete information requested on this PK sheet for each sample. Remember to record all sampling times (use the 24 hour clock; for example, 1:00 PM = 13:00). Add comments, as necessary. Place the samples on ice until centrifugation.
- Plasma: should be separated by centrifugation at 10°C (10 min at 1000 g or 2500 rpm) within four hours after collection. Separated plasma should be transferred to screw capped polypropylene tubes (i.e. Nunc 3.6 ml #379189, 366524 or equivalent) and labeled with the TACL registration number, date and time of sampling, and sample number. Plasma samples should be stored in the dark at -70° C.

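### The PK precision statement in Section 9.4.4 rests on a second stage and 25/30 patients that the current design does not set, and it claims a day 15 trough from all patients although Cohort C has none

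*Combined protocol and SAP*

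**What the plan says.** Section 9.4.4 takes an adult CV of about 100% for trough vincristine. It states a CV of 17% for the estimated mean trough at each of two time points (day 8 and day 15), with 95% confidence bounds within 40%. The condition is "assuming that the study proceeds to the second stage, and that 25/30 patients are evaluable for PK assessment". It concludes that this is precise enough for a meaningful comparison with outside adult and paediatric data.

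On who is sampled, 9.4.4 says that the day 8 and day 15 samples, "representing vincristine trough levels, will be obtained on all patients". Earlier in the same paragraph those samples are limited to arms A and B, and arm C is given only a pre-dose sample and "a trough level at day 8 during the first cycle". Section 7.4.2 agrees that in Cohort C "a trough level will be drawn anytime on day 8", with no day 15 sample. The Appendix 7 worksheet marks "Dose 3 (Not required for Arm C" and labels its day 15 row for arms A and B.

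On sample size, Section 9.0 sets 6 evaluable patients per cohort and dose level for Phase I and says: "The maximum sample size in any cohort at a particular dose level is 12 evaluable patients". That maximum includes 6 for expansion. Section 9.2 gives the same 6 to 12 and describes Phase I accrual, a halt, and then expansion.

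**The concern.** A precision statement is useful only if its sample size is one the design can deliver. Here neither the second stage nor the total of 30 appears in the design sections, so a reader cannot tell what precision the current plan offers.

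The sampling error compounds this. The precision is claimed at each time point, and a day 15 trough exists only in Cohorts A and B, so the group behind that estimate is smaller than the paragraph implies. The other parts of Section 9.4 call the success and response estimates imprecise because the cohorts are small. PK alone is described as precise enough, on a number the design does not set.

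A further mismatch affects how many Cohort C samples exist. Section 9.4.4 places the day 8 trough in the first cycle, whereas the Section 7.1 table says: "Arm C will be obtained prior to Dose 1 and a trough level on day 8, during each cycle". Appendix 7 asks for a second form if arm C has a second cycle, which agrees with Section 7.1.

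**Working it through.** **Inputs.** Between-patient CV 100% (9.4.4); n=25 (9.4.4); 6 to 12 evaluable patients per cohort and dose level (9.0, 9.2); day 15 trough in A and B only (9.4.4, 7.4.2, Appendix 7); day 8 trough in A, B and C.

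**Method.** On the log scale, SD = sqrt(ln(1 + CV²)) = sqrt(ln 2) = 0.8326. The SE of the log mean is 0.8326/sqrt(n), read as the CV of the estimated (geometric) mean. The 95% bounds are exp(±1.96 × SE), as multiples of the estimate.

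**The plan's own figure.** n=25: SE = 0.8326/5 = 0.1665, or 16.7%. exp(1.96 × 0.1665) = 1.386, and the lower bound is 0.72. Both printed figures (17%, within 40%) are reproduced.

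**Group sizes from the current design**, with one dose level per cohort and every evaluable patient giving a usable sample:
- Day 15, A+B: 2 × 6 = 12 to 2 × 12 = 24.
- Day 8, A+B+C: 3 × 6 = 18 to 3 × 12 = 36.
- One cohort: 6 to 12.

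| Group | n | SE | 95% CI, multiple of estimate |
|---|---|---|---|
| Printed case | 25 | 16.7% | 0.72 to 1.39 |
| Day 15, A+B, full expansion | 24 | 17.0% | 0.72 to 1.40 |
| Day 15, A+B, Phase I only; or one cohort, full expansion | 12 | 24.0% | 0.62 to 1.60 |
| One cohort, Phase I only | 6 | 34.0% | 0.51 to 1.95 |
| Day 8, A+B+C, Phase I only | 18 | 19.6% | 0.68 to 1.47 |
| Day 8, A+B+C, full expansion | 36 | 13.9% | 0.76 to 1.31 |

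**Smallest n for an upper bound of +40%.** (1.96 × 0.8326 / ln 1.4)² = (1.632/0.3365)² = 23.5, so 24. For day 15 at one dose level this is exactly the A+B ceiling. For day 8 it lies inside the 18 to 36 range.

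**Dose mix in the day 8 group.** Section 9.0 currently has A and B at 1.5 mg/m² and C at 2.0 mg/m², so the 18 to 36 patients mix two doses unless all cohorts are at the same level.

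**The case against.** **The paragraph resolves itself on sampling.** The sentence about all patients contrasts mandatory troughs with optional Day 1 samples and refers to samples before the second and third doses. A Cohort C cycle has one Marqibo dose, and the same paragraph has already limited these samples to A and B. This stands in part: the site-facing tables are clear, and the documents do not suggest that a site would draw a day 15 trough in Cohort C. The sentence is still wrong as written, and the precision claim follows from it.

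**Around 25 patients is attainable.** The second stage may loosely mean the expansion, and 30 lies within 18 to 36. Section 9.0 adds: "Dose escalation for Cohort B and de-escalation for Cohort C may still occur per study design". Patients replaced under 9.3.1 may also have given PK samples, and combining dose levels would add more. All of this stands, so a reader should not infer that n=25 is impossible. The number is simply not tied to the design.

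**A reader might infer that the 17% is an arithmetic error**, because 100%/sqrt(25) = 20%. The documents do not support that: the log scale gives both printed figures. Nor does a t-based interval show a failure. It gives 1.41 even at the printed n=25, so the gap comes from the choice of t over z.

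**The unstated scale and handling of dose levels** are missing detail for an exploratory objective, not contradictions. A reader might also take Section 9.2 to show that Cohort B has treated patients at both doses. It reports two patients enrolled at the higher level before de-escalation, and it does not report any treated at the lower one.

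**Conclusion.** The point holds and is minor. The precision in 9.4.4 depends on a condition that is absent from the current Section 9, and its statement that all patients give both troughs contradicts its own text, Section 7.4.2 and Appendix 7.

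At one dose level the day 15 estimate meets the stated precision only if Cohorts A and B both expand fully and every patient contributes. A single cohort at one dose level does not meet it. The day 8 estimate meets it from 24 patients upward, with doses mixed unless all cohorts are at one level.

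These results assume the document's CV of 100%, the log-scale normal method that reproduces its figures, and PK counts equal to primary-evaluable counts; larger PK counts are possible. They rest on Section 9 as supplied. Sections 2.4.1 and 2.4.2 on experience to date were not available, so actual accrual is not used here. The consequence is limited because PK is exploratory and the sites' sampling tables are not affected by the precision statement.

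**What to change.** 1. In 9.4.4, delete the references to a second stage and to 25/30 patients.
2. Limit the day 8 and day 15 pair to arms A and B and state day 8 only for arm C. Reconcile the first-cycle wording in 9.4.4 with the each-cycle wording in 7.1 and the second-cycle note in Appendix 7.
3. Restate precision by the document's own method, for example: *With a between-patient CV of about 100% (log scale, normal approximation), the SE and 95% CI for the mean day 15 trough (arms A and B) run from 24.0%, 0.62 to 1.60 times the estimate with 12 patients, to 17.0%, 0.72 to 1.40 with 24. For day 8 (arms A, B and C) they run from 19.6%, 0.68 to 1.47 with 18 patients, to 13.9%, 0.76 to 1.31 with 36.* Note that the day 8 group mixes dose levels unless all cohorts are at the same one.
4. Make the sentence claiming sufficient precision conditional on the number available in the group analysed, and describe single-cohort estimates as imprecise.

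The cost is wording only, with no new samples. The stated precision becomes less favourable for day 15 and for single cohorts.

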9.5 Interim Monitoring of Toxic Death

The occurrence of toxic death (TD) per 9.3.4 will be a primary endpoint for safety monitoring. Based on prior studies, a 10% TRM rate in patients with advanced ALL is expected (see section 2.3). Hence a population toxic death rate that exceeds 10% will be considered unacceptable. No formal statistical monitoring will be employed. Rather, an observed TD rate that exceeds 10% at any time in any cohort will result in immediate suspension of the study, at which time the cause and circumstances of the death and its attribution to the study regimen will be reviewed with the study committee and with the Data and Safety Monitoring Committee (DSMC) to determine

whether modifications to or termination of the study is warranted. Operationally, this criterion will be satisfied if within a cohort, a TD is observed, and the nominal rate exceeds 10%.

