9.2 Study Design

An open label design over two Marqibo® dose levels will be used to evaluate its substitution for vincristine in three different treatment cohorts: (A) patients treated with UK ALL R3, (B) patients treated with UK ALL R3 that omits Mitoxantrone, and (C) patients treated with a modified ALL maintenance regimen. Prior data on relapse ALL patients treated with standard UK ALL R3 and with COG protocol therapies (section 2.3) suggest that approximately 10% of patients treated in first relapse will experience grade 3 or higher toxicity sufficient to prevent the start of subsequent therapy by day 49. Data from patients treated in second or greater relapse, which will represent

the majority of patients on this study, suggest higher delay rates, but are imprecise due to the small number of patients.

For Cohort A, the original design criteria for escalation to DL2 ($\leq 2/6$ not successfully treated at DL1) has been satisfied. Hence, following Amendment #2, a minimum of 6 and a maximum of 12 patients (including 6 for expansion) who are evaluable for the primary endpoint will be enrolled at DL2. Following Amendment #3, Cohort A was dose de-escalated to DL1 given the development of two DLTs at DL2.

Since treatments in Cohorts B and C were expected to be less toxic than Cohort A, as detailed below Cohorts B and C initially opened to accrual at DL2.

For Cohort B, dosing began at DL2. The cohort was subsequently de-escalated to DL1 after 2 patients were enrolled. The decision to dose de-escalate was an elective decision made by the study committee in the context of known hepatic toxicity associated with Marqibo®, the development of hepatic DLT in one subject on this cohort, and a second subject who was close to meeting criteria for DLT based on hepatic function tests. Cohort B will remain open to accrual at DL1 with 6-12 evaluable patients. Cohort B may be re-escalated to DL2 pending further experience at DL1 ($\leq 2/6$ not successfully treated in the first 6 evaluable patients).

For Cohort C, dosing began at DL2. Cohort C will remain open to accrual at DL2 with 6-12 evaluable patients, provided the primary endpoint conditions are met, ie, $\leq 2/6$ not successfully treated in the first 6 evaluable patients at this dose level. If Cohort C is de-escalated, the cohort may continue to accrue at DL1 between 6 to 12 evaluable patients at that dose level.

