The occurrence of unsuccessful treatment, following the definition in Section 9.1.1, will be monitored in real time during the Phase I and expansion accruals. The design will not be prescriptive. Rather, if at any time after the third patient is enrolled either within a single cohort or in all cohorts combined, if nominally more than 1/3 of evaluable patients within a single cohort or in all cohorts combined are not successfully treated the study will be suspended pending review by the study committee of the types and severity of toxicities in all three cohorts, with possible determinations to continue at the specified dose level in all three cohorts, to de-escalate the dose of Marqibo® to DL1 in one or more cohorts, or to halt the study in one or more or cohorts, with appropriate amendments as necessary. In addition, during Phase I, the decision to de-escalate will be considered separately for each cohort and dose level when more than 1 patient is treated unsuccessfully after the first 6 evaluable patients have been enrolled. And the decision to escalate during Phase I will be considered separately for each cohort and dose level when no more than 1 patient is treated unsuccessfully after the first 6 evaluable patients have been enrolled. Accrual to the study will be halted, before reopening for expansion, once at least 6 evaluable patients have been treated at the final tested dose level in each of the three cohorts.

Treatment success, as defined in in Section 9.1.1, during the first course of treatment will continue to be monitored during the expansion. Assuming a treatment failure rate that exceeds 10% (i.e., $p_0 > 0.10$) is unacceptable, a Bayesian monitoring rule based on a pessimistic Beta (1,4) prior distribution will be used to judge the empirical evidence from both the Phase I and expansion

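### The toxic-death and >1/3 failure pausing rules count by cohort without naming dose level, so read literally a first toxic death soon after Cohort B returns to DL2 may not pause the study

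*Combined protocol and SAP*

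**What the plan says.** Cohort and dose level are separate factors in this design: "An open label design over two Marqibo® dose levels will be used to evaluate its substitution for vincristine in three different treatment cohorts". Section 9.0 sets sample sizes by cohort and dose level, and section 9.2 does the same for one decision rule: "the decision to de-escalate will be considered separately for each cohort and dose level". That rule applies once 6 evaluable patients have been enrolled at the level, and more than 1 failure brings de-escalation up for consideration.

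The two suspension rules are worded differently.

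- **Failures (9.2).** Monitoring starts "if at any time after the third patient is enrolled either within a single cohort or in all cohorts combined", and the trigger is "if nominally more than 1/3 of evaluable patients within a single cohort or in all cohorts combined are not successfully treated".
- **Toxic death (9.5).** "an observed TD rate that exceeds 10% at any time in any cohort will result in immediate suspension of the study". The operational form is "Operationally, this criterion will be satisfied if within a cohort, a TD is observed, and the nominal rate exceeds 10" per cent.

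Neither rule mentions dose level, and 9.2 does not say whether the third-patient count restarts at a new level.

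Mixed-dose cohorts already exist. Section 9.2 reports that Cohort A met its DL1 criterion, had two DLTs at DL2 and returned to DL1. Cohort B enrolled 2 patients at DL2, one with a hepatic DLT, and moved to DL1. It may go back up: "Cohort B may be re-escalated to DL2 pending further experience at DL1".

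**The concern.** A pausing rule based on an observed rate depends on its denominator. If patients treated at another dose level are counted, event-free patients at the lower dose dilute an early signal at the higher one. Events at the higher dose also carry over to patients now on the lower one.

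Toxic death is the more exposed of the two, because it has no dose-level trigger anywhere in the plan. What would be lost is the mandatory suspension and the DSMC review that 9.5 attaches to a rate above 10%, at the point where experience at the dose is thinnest. How the success rate is estimated at the end is not affected.

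**Working it through.** The plan states no error rate for either rule, so there is no figure to reproduce. I applied the rules as written.

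**Inputs.** Cohort B has 2 patients at DL2, one with a DLT (9.2), and 6 evaluable patients are planned at DL1 (9.0). The thresholds are above 10% (9.5) and above 1/3 (9.2).

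**Assumptions.** No toxic death among the first 8 patients. Both DL2 patients were evaluable and only one failed. DL1 gives 0/6 failures, which meets every escalation threshold stated in 9.2. Events are counted in enrollment order.

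**1. First toxic death after return to DL2**

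| Re-escalated patient | Cohort-wide | DL2 only |
|---|---|---|
| 1st | 1/9 = 11.1%, suspends | 1/3 = 33.3%, suspends |
| 2nd | 1/10 = 10.0%, no | 1/4 = 25.0%, suspends |
| 7th | 1/15 = 6.7%, no | 1/9 = 11.1%, suspends |
| 8th | 1/16 = 6.3%, no | 1/10 = 10.0%, no |

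**2. Chance of a toxic-death pause over the first 7 re-escalated patients, true rate q**

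By dose level, any death suspends: 1 − (1−q)^7.

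- q = 0.10: 1 − 0.9^7 = 0.522
- q = 0.20: 1 − 0.8^7 = 0.790

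Cohort-wide, a pause needs a death in the first re-escalated patient or two deaths among the seven. Two deaths always suffice, since at most 15 patients have been treated and 2/15 = 13.3%. The chance is 1 − (1−q)[(1−q)^6 + 6q(1−q)^5].

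- q = 0.10: 1 − 0.9 × (0.5314 + 0.3543) = 0.203
- q = 0.20: 1 − 0.8 × (0.2621 + 0.3932) = 0.476

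**3. Failures after return to DL2 (single-cohort arm)**

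| Failures on return | Cohort-wide | DL2 only |
|---|---|---|
| 1/1 | 2/9 = 22.2%, no | 2/3 = 66.7%, above 1/3 |
| 2/2 | 3/10 = 30.0%, no | 3/4 = 75.0%, above 1/3 |
| 3/3 | 4/11 = 36.4%, suspends | 4/5 = 80.0%, above 1/3 |

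Dilution shrinks as DL1 failures rise. With 1/6 at DL1, one failure on return reads 3/9 = 33.3% (no) and two read 4/10 = 40% (suspends). With 2/6, the cohort is already at 3/8 = 37.5% before any return. The all-cohorts arm cannot be worked out, because the number treated in Cohort A at DL2 is not in the text available to me.

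**4. Carry-over to DL1.** One failure in the first 3 DL1 patients is 1/3 at DL1, not above 1/3. Cohort-wide it is (1+1)/(2+3) = 2/5 = 40% and triggers review. At a true 20% failure rate, checking after each of 6 DL1 patients (from the third at DL1 for the dose-level version), the chance of suspension is 0.263 by dose level and 0.541 cohort-wide.

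**The case against.** Several points on the other side have force.

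- **Pooling is not stated.** A reader might infer that the plan deliberately pools dose levels. It does not say so. The text is silent, and 9.2 also uses the word cohort for the Phase I and expansion groups. What holds is that the denominator is not specified by dose level, and that the literal reading pools.
- **Failures at a new dose do not go unnoticed.** A reader might infer that 0/6 at DL1 followed by 3/3 at DL2 passes unflagged at 3/9. No open cohort fits that pattern. Cohort A now enrolls at DL1 only, Cohort C began at DL2 and can only go down, and Cohort B's earlier DL2 failure brings it to 4/11, which suspends. The dose-level rule of more than 1 failure in 6 is also untouched by pooling, though it acts only after six evaluable patients.
- **Other safeguards exist.** A reader might infer that nothing else acts early. DLTs are reported immediately (4.2), all Grade 5 events need expedited reporting (11.3), and the study team evaluates serious events at once (12.2). Cohort B was de-escalated after 2 patients by committee choice. These routes are real, but they are not numeric triggers and do not guarantee suspension and DSMC review.
- **Carry-over costs little.** A reader might infer that the study could be halted for a dose no longer in use. Section 9.2 describes its design as non-prescriptive, so the result is a review. DL2 is also still in use in Cohort C and possible again in Cohort B.
- **The 10% is a population benchmark.** Section 9.5 ties it to expected mortality in advanced ALL. That is a good reason to keep the cohort-wide check, but it does not argue against adding a dose-level one.

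**Conclusion.** The point holds for toxic death, and more weakly for failures. As worded, a first toxic death from the second re-escalated Cohort B patient onward does not trip 9.5. At a true 20% death rate, the chance of a pause within 7 such patients is about 48%, against 79% with a dose-level count. For failures, the single-cohort arm misses 2/2 on return (3/10) but catches 3/3 (4/11). Carry-over to DL1 amounts mainly to an extra review.

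This rests on the literal reading of cohort, on Cohort B actually being re-escalated, on no toxic death among its first 8 patients, and on the stated DLT being its only DL2 failure with both DL2 patients evaluable. If both DL2 patients had failed, 2/2 on return would read 4/10 and suspend. The documents do not support the claim that the failure rule is generally blind after an escalation.

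**What to change.** **Section 9.5.** Replace *within a cohort* by *within a cohort and dose level, or within a cohort overall*.

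**Section 9.2.** Add a >1/3 check within each cohort and dose level, starting at the third evaluable patient at that level and counting everyone ever treated at that level in that cohort. Keep the cohort and all-cohorts checks unchanged. Do not strip failures at a vacated dose out of the combined check while leaving those patients in the denominator, since that would itself dilute the rate. Carry-over therefore remains, at the price of a review in which the committee can see results by dose.

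**Cost.** The text change is two sentences, and dose level is already assigned at enrollment (3.2). The operating cost is more pauses. For the first 7 re-escalated Cohort B patients at a true 10% toxic-death rate, the chance of a pause rises from about 20% to 52%. That is of a kind the plan already accepts, because over the first 9 patients of any cohort the present rule pauses with probability 1 − 0.9^9 = 61% at the same rate. On the failure side, with 1/2 already at DL2, a failure in the first re-escalated patient (2/3) would by itself prompt a review.
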